4.1 Study Objective

The study objective is to evaluate the safety and efficacy of the Visualase MRI-Guided Laser Ablation System ("Visualase System") for necrotization or coagulation of epileptogenic foci in patients with intractable MTLE.

4.2 Study Endpoints

One primary safety endpoint, one primary efficacy endpoint, 8 secondary endpoints, will be used to evaluate the study objective.

4.2.1 Primary Safety Endpoint

The primary safety endpoint is the incidence of qualifying device-, procedure-, or anesthesia-related adverse events (defined in Appendix 2) through 12 months following the Visualase procedure.

4.2.2 Primary Efficacy Endpoint

The primary efficacy endpoint is seizure freedom (defined as Engel Class I, Appendix 1) at 12 months following the Visualase procedure.

4.2.3 Secondary Endpoints

- 1. Seizure freedom (defined as Engel Class I, Appendix 1) at 12 months following the Visualase procedure compared to historical reference threshold for continued medical therapy
- 2. Seizure freedom (defined as Engel Class I, Appendix 1) at 12 months following the Visualase procedure, including subjects who are retreated with Visualase

[figure not shown]
Form

[figure not shown]
Revision 1.0

Page 5 of 23

Medtronic

- 3. Within-subject change of Boston Naming Test score (English language version), from baseline to 12 months following the Visualase procedure
- 4. Within-subject change of Rey Auditory Verbal Learning Test 5-Trial Total score (English language version), from baseline to 12 months following the Visualase procedure
- 5. Within-subject change of Quality of Life in Epilepsy inventory (QOLIE-31) score (English language version), from baseline to 12 months following the Visualase procedure
- 6. Within-subject change of SF-36 quality of life questionnaire Mental Component Score (English language version), from baseline to 12 months following the Visualase procedure
- 7. Within-subject change of SF-36 quality of life questionnaire Physical Component Score (English language version), from baseline to 12 months following the Visualase procedure
- 8. Seizure freedom (defined as Engel Class I, Appendix 1) at 12 months following the Visualase procedure compared to historical reference threshold for open surgical resection

5. Investigation Plan

This is a prospective, single-arm, multicenter, investigational clinical study. Following informed consent, subjects' qualification for the Visualase procedure will be confirmed by a central review committee (Pre-Surgical Evaluation). Baseline assessments will also be performed at any time prior to the Visualase procedure.

Subjects will then undergo MRI-guided laser ablation of the amygdala and hippocampus with the Visualase System. Subjects will be followed for 12 months following the Visualase procedure and assessed for adverse events, seizures, neuropsychological outcomes, mood, and quality of life outcomes. Figure 1 below illustrates the study design.

[figure not shown]

[figure not shown]
Figure 1. SLATE Study Design

The study subject population consists of adult patients with medically intractable (per the definition by the International League Against Epilepsy (Kwan 2010) MTLE, with radiological and electrophysiological evidence consistent with unilateral focal seizure onsets. A full listing of inclusion and exclusion criteria is contained within the SLATE Clinical Investigational Plan (CIP).

Reference rates taken from the literature will serve as expected safety and efficacy rate for the primary endpoint. Attiah *et al.* (2014) published a decision analysis to calculate the seizure freedom rate and late mortality/morbidity rate that laser ablation for temporal lobe epilepsy would need to demonstrate to provide quality of life (QOL) improvements equivalent to anterior temporal lobectomy (ATL). The meta-analysis included records of over 25,000 cases of ATL and the available data for laser ablation from a recent multicenter study. The results of the analysis revealed that subjects achieving 43% Engel I

Revision 1.0

Page 7 of 23

outcomes and no more than 40% late mortality/morbidity with laser ablation is needed in order to be grossly equivalent (as defined by the author) to ATL. Therefore, this study compares safety and efficacy outcomes of laser ablation to the 43% seizure freedom and 40% qualifying AE rate threshold of gross equivalence determined by Attiah *et al.* (2014).

Seizure control is expected to yield improvements in health-related quality of life. Primary and secondary endpoints of this study have been designed to evaluate these outcomes. Additional secondary endpoints have been designed to further evaluate the cognitive outcomes after the Visualase procedure.

The study design is limited by the absence of an active control arm. Refer to section 3.2 of CIP.

6. Determination of Sample Size

The primary efficacy endpoint is the 12-month seizure-free rate. The analysis of the primary efficacy endpoint will compare the lower 2-sided exact 95% confidence interval (CI) boundary of the observed rate against 43%. The lower bound of the seizure freedom rate CI following the Visualase procedure must exceed 43%. Based on published and unpublished accounts of seizure freedom rates following laser ablation for MTLE, it is expected that approximately 56% of subjects who undergo the Visualase procedure will be seizure free through 12 months post-procedure. Given the assumption of a 56% success rate with Visualase, 89% power can be achieved with 150 treated subjects to show that the success rate after Visualase is superior to 43%.

Subjects will be considered enrolled upon the signing of a consent form. It is anticipated that once enrolled, some subjects will not proceed to the Visualase procedure due to failure at their pre-surgical evaluation, changes in clinical status, or non-compliance to protocol. Based on these factors, and on previous reports of attrition in similar studies, the assumed attrition rate is 30%. To account for this attrition, up to 215 subjects may be enrolled to ensure at least 150 subjects are treated with the Visualase procedure.

Certain secondary endpoint assessments will be made using subject questionnaires. These self-reported instruments are influenced by primary language. Validated translations are not available in all languages; thus, enrollment will be limited to subjects who can complete these assessments in either English or Spanish. Further, the impact of grouping across translations for analysis is an important consideration. Therefore, for the specified secondary cognitive and QOL endpoints, the subset of only the English-language versions will be used for analysis. To preserve adequate statistical power for analysis of this subset, the total Spanish language enrollment will be restricted to no more than 40% of the total study-wide enrollment population. A 40% cap was chosen based on a conservative assumption that only 73% of subject data are usable, resulting in an evaluable sample of N=109. If only 50% of this sample were used for secondary endpoints restricted to English language (N=55), the power to detect a change in the neuropsychological assessments would be 86%, based on best-estimate effect size.

7. General Statistical Considerations

7.1 Study Subjects

7.1.1 Disposition of Subjects

Subject disposition throughout the course of the study will be summarized using a flow chart (e.g., CONSORT flow diagram).

7.1.3 Analysis Sets

The following Analysis Sets ("populations") will be used for analysis of SLATE data.

7.1.3.1 Safety Population

All subjects who sign a consent form (i.e., are enrolled) will be included in the safety population.

All summaries of safety data will be based on the safety population.

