6.4 Minimization of Bias

Selection of subjects, treatment of subjects, and evaluation of study data are potential sources of bias. Methods incorporated in the study design to minimize potential bias include (but are not limited to):

1. Subjects will be screened to confirm eligibility for enrollment with defined inclusion/exclusion criteria prior to enrollment.

- 2. A central review of subjects' epilepsy history, MRI and EEG will be performed to confirm study qualification for the Visualase procedure.
- 3. Subject demographics will be collected pre-procedure in order to later assess possible characteristics that may influence endpoints.
- 4. Subjects will serve as their own controls for selected secondary endpoints.
- 5. A statistical analysis plan, which will document all pre-specified analyses and analysis methods, will be developed prior to analyzing data.
- 6. A modified intent-to-treat analysis will be performed on the study endpoints.
- 7. All study sites will use the same version of the Clinical Investigational Plan and Case Report Forms (CRFs).
- 8. All study personnel and Medtronic personnel will be trained on their respective aspects of the study using standardized training materials.
- 9. All study personnel will be trained on and required to follow the Clinical Investigational Plan.
- 10. An independent Data Monitoring Committee (DMC) will be used to safeguard the interests of study subjects, and to act as an advisory panel ensuring continued scientific validity and necessity. (See Appendix D.)
- 11. All study investigators will be required to meet 21 CFR Part 54, Financial Disclosure by Clinical Investigators.
- 12. All neuropsychological assessments will be scored at a core laboratory.
- 13. Volumetric analysis of tissue ablation will be conducted at a core laboratory.

In summary, potential sources of bias that may be encountered in this clinical study have been considered and minimized by careful study design.

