7.1.3.2 Modified Intent to Treat (mITT) Population

All subjects who enter the operating room and start the Visualase procedure (i.e., undergo scalp incision) will be included in the mITT analysis population. The mITT population will be the primary analysis population for efficacy evaluations.

Non-compliance is defined as any subjects who have not submitted enough seizure diaries or qualifiers in their seizure diaries through 12 months, from which the Engel I Classification could not be determined at study exit because of the missing information. The detail of the seizure diaries refers to section 7.5.1 of CIP.

SLATE Statistical Analysis Plan Revision 1.0 Page 9 of 23 Medtronic

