7.9.1.1 Hypotheses

It is hypothesized that the upper bound of the 95% CI for the proportion of subjects experiencing any qualifying device-, procedure-, or anesthesia-related adverse events (per Appendix 2) through 12 months following the Visualase procedure will be less than 40%. The hypotheses associated with this endpoint are as follows:

Null Hypothesis: $\pi V \ge 0.4$

Alternate Hypothesis: $\pi V < 0.4$

Where πV is the proportion of subjects treated with Visualase experiencing any qualifying AE.

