7.9.1.3 Analysis Methods

An exact 95% CI (Clopper 1934) will be calculated to determine if the upper bound of the CI for qualified AEs is less than 40%.

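### The visible text conflicts on the denominator of the 40% primary safety test: everyone who consented, or those treated

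*SAP*

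**What the plan says.** Two groups of statements bear on the denominator.

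**Towards all consented subjects.** SAP 7.1.3.1: "All subjects who sign a consent form (i.e., are enrolled) will be included in the safety population", and "All summaries of safety data will be based on the safety population". Protocol 14.3.1 has the same rule. SAP 7.1.3.2 gives mITT a role only on the other side: "The mITT population will be the primary analysis population for efficacy evaluations".

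**Towards treated subjects.** SAP 7.9.1.1 (and protocol 14.4.1) define the tested parameter as "the proportion of subjects treated with Visualase experiencing any qualifying AE". The endpoint window in SAP 4.2.1 runs "through 12 months following the Visualase procedure". Protocol 6.4, in its list of bias-control measures, states: "A modified intent-to-treat analysis will be performed on the study endpoints". Protocol 7.14 says that subjects whose procedure is aborted without rescheduling are followed for an mITT analysis that covers adverse events as well as seizures.

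**Silent.** SAP 7.9.1.3 and protocol 14.4.3 call for an exact interval to "determine if the upper bound of the CI for qualified AEs is less than 40" percent, and name no analysis set.

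The mITT set is fixed at incision: subjects who "start the Visualase procedure (i.e., undergo scalp incision) will be included in the mITT analysis population".

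**The concern.** A programmer working from the SAP alone finds one set linked to safety data, and it is everyone who consented. The plan expects 30% of those subjects never to reach the procedure. A qualifying event must be related to the device, the procedure or the anesthesia (SAP Appendix 2), and procedure-relatedness starts at the first scalp incision (protocol Table 6). Untreated subjects would therefore enlarge the denominator and add almost nothing to the numerator. The main exception is an anesthesia-related event in a procedure stopped before incision.

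That dilution can only favour the device. It would understate the reported primary safety rate, and the 95% interval would no longer control the error rate for the parameter in the hypothesis. The effect stays within this endpoint, because SAP 7.5 gates the secondary hierarchy on primary efficacy alone.

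**Working it through.** **Inputs.** At least 150 treated, up to 215 enrolled, 30% attrition (SAP 6). Success if the upper limit of the two-sided exact 95% interval is below 40% (SAP 7.9.1.3). Assumptions: exactly 150 treated, and no qualifying events in untreated subjects. The figure of 160 consented is my illustration of low attrition; it is not in the documents.

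**The plan's own figures.** Enrollment: 150 / 0.70 = 214.3, rounded up to 215. Efficacy power: the exact lower limit first exceeds 43% at 77/150 (43.05%), and P(X ≥ 77 | n = 150, p = 0.56) = 89.1%. Both match the plan. No power or expected event rate is visible for the safety test.

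**Passing limits.** The upper limit for x events in n subjects is the 0.975 quantile of Beta(x + 1, n − x). The largest x with an upper limit below 40% is:

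| Denominator | Largest passing count | Upper limit | Upper limit with one more event |
|---|---|---|---|
| 150 (treated) | 47 (31.3%) | 39.4% | 40.1% |
| 160 (consented) | 51 (31.9%) | 39.7% | 40.3% |
| 215 (consented) | 71 (33.0%) | 39.7% | 40.2% |

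Seventy-one events are 71/150 = 47.3% of the treated.

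**Reported rate.** The relative shrinkage is 1 − 150/N: 6.3% at N = 160 and 30.2% at N = 215. Twelve events, for example, read as:
- 12/150 = 8.0% (95% CI 4.2 to 13.6)
- 12/160 = 7.5% (3.9 to 12.7)
- 12/215 = 5.6% (2.9 to 9.5)

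**Chance of passing.** This is P(X ≤ limit) with X ~ Binomial(150, p), where p is the true treated rate:

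| p | 150 treated | 160 consented | 215 consented |
|---|---|---|---|
| 21.9% | 99.73% | 99.98% | 100% |
| 30% | 67.5% | 87.6% | 100% |
| 40% | 1.8% | 7.7% | 97.2% |

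**How likely a changed result is.** Pass and fail differ only if the treated have at least 48 events (32%) and no more than the consented-set limit. Protocol 3.2 lists 6 complications in 37 patients: 2 hemianopias, 2 hemorrhages (one asymptomatic), and 2 transient events. If the hemianopias were permanent, the other hemorrhage qualified, and these were separate patients, 3/37 = 8.1% would qualify (exact 95% CI 1.7 to 21.9). At the upper end, 21.9%, the two denominators disagree with probability 100% − 99.73% = 0.27% at 215 consented. At 30% the figure is 87.6 − 67.5 = 20.1% at 160 and 100 − 67.5 = 32.5% at 215.

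**Edges of the treated set.** Dropping 1, 3 or 5 subjects aborted after incision from 150 gives limits of 47/149, 46/147 and 46/145. Adding 1, 2 or 3 pre-incision anesthesia events to numerator and denominator gives 48/151, 48/152 and 48/153. Neither choice matters much.

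**The case against.** The best reply is that the plan already answers the question. The hypothesis names treated subjects, and the interval is naturally the interval for that proportion. A window counted from the procedure has no meaning for someone who never had one. Protocol 6.4 does not restrict mITT to efficacy, and protocol 6.2 lists the primary safety endpoint among the study endpoints. SAP 7.10 separately describes descriptive adverse event tables, so the rule on safety summaries may refer only to those; event collection begins at consent (protocol 10.2.1), which makes consent-based tables sensible. The visible text is also incomplete where it matters: protocol 14.3.1 has a gap, and 14.3.3 and 14.3.4 appear in the contents but cannot be read.

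Most of this stands, and it makes the treated reading the more likely one. A reader might infer that the plan assigns the 40% test to all consented subjects, or that nothing links safety to mITT. The documents support neither. What remains is that the support for the treated reading is indirect: a bias-control list, a follow-up rule for aborted procedures, and a parameter definition. Against it stands an explicit population rule worded to cover all safety summaries, and no visible sentence in the test's own section chooses between them.

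**Conclusion.** The visible passages conflict, and the denominator of a primary endpoint should not depend on how a reader weighs them. Treated subjects is the more likely intention, and text that cannot be seen may confirm it.

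Under the all-consented rule the practical effect would be mainly an understated rate, by up to 30% in relative terms at 215 consented and less if fewer untreated subjects enroll. A reader might take the 97.2% chance of passing at a true rate of 40% as the trial's actual error rate. It is not: it needs the less likely reading, the planning maximum of 215, and a true rate far above the prior series. At rates up to 21.9% a changed pass or fail result has probability of at most 0.27%. That estimate rests on a small series and on the assumptions above about which of its events would qualify. The point is worth fixing because the correction is nearly free and follows the plan's own hypothesis.

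**What to change.** In SAP 7.9.1.3 and protocol 14.4.3, state that the Clopper-Pearson test against 40% uses the mITT set, defined by scalp incision, so that procedures aborted after incision count as treated. This is a choice; its merit is that the set then begins where procedure-relatedness begins. In SAP 7.1.3.1 and protocol 14.3.1, limit the all-consented set to descriptive adverse event summaries and listings, including pre-operative events. If the full protocol text already says this, repeat it in SAP 7.9.1.3.

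Optionally, add a sensitivity analysis that puts any qualifying anesthesia-related event before incision into both numerator and denominator.

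The cost is a few sentences and no new data. The reported rate will be less favourable than on the larger denominator.

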7.1.3.2 Modified Intent to Treat (mITT) Population

All subjects who enter the operating room and start the Visualase procedure (i.e., undergo scalp incision) will be included in the mITT analysis population. The mITT population will be the primary analysis population for efficacy evaluations.

Non-compliance is defined as any subjects who have not submitted enough seizure diaries or qualifiers in their seizure diaries through 12 months, from which the Engel I Classification could not be determined at study exit because of the missing information. The detail of the seizure diaries refers to section 7.5.1 of CIP.

SLATE Statistical Analysis Plan Revision 1.0 Page 9 of 23 Medtronic

7.2 General Statistical Methods

Statistical analyses will be performed using SAS Software, Version 9.4 or later. Continuous variables will be summarized by N, mean, standard deviation, median, quartile1 and quartile3, minimum, and maximum. Categorical variables will be described by number and percentage. For binary endpoints, a 95% exact CI will be provided.

All statistical tests will be conducted at a two-sided alpha level of 0.05, unless otherwise stated.

This SAP includes a comprehensive description of the statistical methods and reports to be included in the final study report.

7.3 Center Pooling

This study may include up to 25 US centers. Data from all the centers will be pooled. For each tested study endpoint, center effect will not be considered in the statistical modeling. Center-specific analyses are considered to be post hoc and exploratory.

7.4 Handling of Missing, Unused, and Spurious Data and Dropouts

7.4.1 Missing Data

Missing primary efficacy endpoint values and missing secondary endpoint values associated with testable hypotheses will be imputed for analysis with the mITT analysis population. Missing primary efficacy endpoint data will be imputed as a binary outcome of seizure freedom, regardless of missing pattern. No daily level imputation will be conducted.

The primary method of imputation will be multiple imputation (SAS PROC MI followed by MIANALIZE). Ten repetitions will be performed and, if needed, will be increased until the algorithm converges.

The Markov chain Monte Carlo (MCMC) method or Fully Conditional Specification (FCS) will be used with the default number of burn-in iterations before the imputation. The model variables will include: age, sex, race (white, African American, or other), and duration of disease.

SLATE Statistical Analysis Plan		Form
Revision 1.0	Page 10 of 23	Medtronic

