14.9 Missing Data

Missing primary efficacy endpoint values and missing secondary endpoint values associated with testable hypotheses will be imputed for analysis with the mITT analysis population. The primary method of imputation will be by multiple imputation (SAS PROC MI and MIANALIZE) using the Markov chain Monte Carlo method. Details of predictor variables to be used in SAS PROC MI, seed number, and number of imputations to be performed will be provided in the SAP.

14.10

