7.9.2.3 Analysis Methods

An exact 95% CI for the percentage of subjects who are seizure free will be calculated.

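### Adding imputations until convergence is not a workable rule, and with no visible seed a primary verdict near 43% can depend on the random draw

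*SAP*

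**What the plan says.** SAP 7.4.1 (Missing Data) makes multiple imputation the primary method for missing primary efficacy values in the mITT population, imputed as a binary outcome. On the number of imputations it says: "Ten repetitions will be performed and, if needed, will be increased until the algorithm converges". It allows either MCMC or fully conditional specification (FCS), with default burn-in, and lists age, sex, race and duration of disease as model variables. It gives no convergence criterion, Monte Carlo error target or maximum number.

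Protocol 14.9 (Missing Data) commits that the predictor variables, "seed number, and number of imputations to be performed will be provided in the SAP". SAP 7.4.1 supplies the predictors and a starting number but no seed. SAP 7.11 declares no changes from the protocol's planned analysis.

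The primary rule is in SAP Section 6: "The lower bound of the seizure freedom rate CI following the Visualase procedure must exceed 43"%. SAP 7.9.2.3 adds: "An exact 95% CI for the percentage of subjects who are seizure free will be calculated". Neither place says how an exact interval is to be combined over imputed datasets. Under SAP 7.5, all eight secondary tests are conditional on the primary efficacy result.

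**The concern.** The number of completed datasets and the convergence of the algorithm are separate matters. An MCMC or FCS chain reaches its stationary behaviour through burn-in and iterations. Drawing more datasets from it only reduces the Monte Carlo error of the pooled result. SAP 7.4.1 leaves the control that matters for convergence at its default and attaches the convergence condition to the one that does not.

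Read literally, the rule never triggers an increase and the number stays at ten. Read practically, someone decides when to stop adding imputations. This is a single-arm study without treatment blinding, and nothing prevents that decision being made after the pooled bound has been seen.

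Without a declared seed, the same data can give different pooled bounds on different runs. Success is a strict pass or fail at 43%, and it opens or closes the whole secondary hierarchy. A result near the limit could then be challenged as a choice of seed or of imputation count.

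**Working it through.** **Inputs.** From the documents: 150 treated subjects, an assumed seizure-free rate of 56%, a pass if the lower 95% bound exceeds 43%, two-sided alpha 0.05 (SAP Section 6 and 7.2), and ten imputations (SAP 7.4.1). Assumed: the share of missing primary outcomes, which the documents do not give. I use 5%, 10%, 20% and 27% (8, 15, 30 and 40 of 150). The top value is borrowed from SAP Section 6, where "a conservative assumption that only 73% of subject data are usable" supports the cap on Spanish-language enrolment.

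**1. The plan's own figure.** The SAP states: "89% power can be achieved with 150 treated subjects to show that the success rate after Visualase is superior to 43"%. The exact lower bound is 42.39% at 76/150 and 43.05% at 77/150, so 77 is the pass mark. P(X ≥ 77 | 150, 0.56) = 0.891, which reproduces the 89%. At a true 43% the chance of passing is 0.0244.

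**2. Size of the seed noise.** Let x be the number seizure-free among n_obs observed, with n_mis missing. Each imputation draws p from Beta(x + 0.5, n_obs − x + 0.5), then the missing successes from Binomial(n_mis, p). Outcomes are missing at random and no covariates are used. The variance of the completed rate between imputations is

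B = n_mis · p(1 − p) · (n_obs + 1 + n_mis)/(n_obs + 2) / 150²,

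and the SD of the pooled rate across seeds is √(B/M), where M is the number of imputations.

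- 10% missing, x = 70 of 135: p = 70.5/136 = 0.518. B = 15 × 0.518 × 0.482 × 151/137 / 22,500 = 0.000183. The SD is 0.43 points at M = 10 and 0.14 at M = 100.
- 27% missing, x = 58 of 110: p = 58.5/111 = 0.527. B = 40 × 0.527 × 0.473 × 151/112 / 22,500 = 0.000597. The SD is 0.77 points at M = 10 and 0.24 at M = 100.

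One more seizure-free subject moves the observed rate by 1/135 = 0.74 or 1/110 = 0.91 points. With ten imputations, seed noise is therefore of the order of one subject. The lower bound varies somewhat more, because B is itself estimated. Its SD across seeds is 0.33 to 1.07 points at M = 10 and 0.10 to 0.30 at M = 100, over 5% to 27% missing.

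**3. Chance that a given result passes.** By Rubin's rules T = U + (1 + 1/M)B, with U the average within-imputation variance. The bound is the pooled rate minus t·√T with Barnard–Rubin degrees of freedom. Simulated over seeds at M = 10:

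- 10% missing: 69/135 passes under 19% of seeds, 70/135 under 72%.
- 27% missing: 57, 58 and 59 of 110 pass under 22%, 55% and 84% of seeds.

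An observed rate at the planned 56% gave the same verdict whatever the seed.

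**4. Chance that two seeds disagree.** This is Σ_x Bin(x; n_obs, 0.56) · 2π(x)(1 − π(x)), with π(x) from step 3. At 10% missing, x = 69 contributes 0.0358 × 2 × 0.19 × 0.81 = 0.0110 and x = 70 contributes 0.0429 × 2 × 0.72 × 0.28 = 0.0173. Neighbouring counts bring the total to 0.030.

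| Missing | M = 10 | M = 100 | M = 500 |
|---|---|---|---|
| 5% | 2.0% | 0.8% | ≤ 0.2% |
| 10% | 3.0% | 0.1% | ≤ 0.2% |
| 20% | 5.7% | 0.9% | ≤ 0.2% |
| 27% | 7.7% | 1.9% | ≤ 0.2% |

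The M = 100 column is not monotone because it depends on how close an attainable count falls to the limit.

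**5. Other pooling rules.** Pooling on the logit scale, an exact interval at the averaged count, and an exact interval on the effective sample size give, with the rule above, 1.9% to 7.8% at M = 10. At M = 100 they give 0.1% to 3.0%. Under the effective-size rule with 27% missing, 58/110 lies almost on the limit, and disagreement stays at 3.0% even at M = 500.

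**6. Error rate and power.** At a true 43%, the chance of passing with ten imputations is about 2.3% to 2.5%. Going from 10 to 100 imputations raises power by about 1 to 3 points, for example from 76.5% to 78.4% at 27% missing.

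**The case against.** The strongest reply is that ten imputations are statistically valid. Rubin's (1 + 1/M) term already allows for a finite number, and step 6 shows no inflation of type I error. Seed noise is also small beside sampling error. The sampling standard error is √(0.56 × 0.44/150) = 4.05 points, or 4.75 at n = 109, so the seed variance is about 1% to 5% of it: (0.33/4.05)² = 0.7% and (1.07/4.75)² = 5.1%. All of this stands. The point concerns reproducibility and pre-specification, not bias.

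A reader might infer from the 73% usable-data figure that the SAP expects 27% of primary outcomes to be missing. It does not. That figure serves the language cap for the cognitive and quality-of-life endpoints, and the 89% power uses all 150 subjects. The plan also limits missing seizure outcomes: retreatment and open resection count as failures (protocol 7.17), late visits are analysed (7.15), and section 7.15.5 permits diary review without an office visit. So 27% is an upper scenario; at 5% missing, disagreement is 2.0%.

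A reader might also conclude that the SAP has no seed at all. The public text passes from 7.4.1 to 7.4.3, so a seed in an unseen 7.4.2 cannot be excluded. It is absent from 7.4.1, where the other promised items appear.

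**Conclusion.** The point holds as a specification gap. The rule for raising the number of imputations is unworkable whatever the missing rate, and the promised seed is not in the visible SAP. The primary verdict can depend on the seed only when outcomes are missing and the result is within a few subjects of the limit. With ten imputations, two seeds disagree in about 2% to 8% of trials at a true 56%, against about 0.1% to 2% with 100. These figures assume 5% to 27% missing at random, no covariates and Rubin pooling.

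The documents do not support the broader reading that the primary result is generally at the mercy of the seed. With no missing outcomes, or with an observed rate near 56%, the seed changes nothing.

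**What to change.** Replace the sentence in SAP 7.4.1 with the following content:

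- A fixed number of imputations, at least 100, and a stated seed, neither to be changed after outcome data are seen. Several hundred reduces disagreement further, to 0.2% or less at 500 under the main pooling rule. The seed makes the result repeatable; only the larger number shrinks the noise.
- Convergence assessed with trace plots, with burn-in lengthened if needed.
- One named algorithm in place of the choice between MCMC and FCS. FCS with a logistic model suits the binary endpoint.
- The rule for pooling the confidence bound over imputations, and how it relates to the exact interval in SAP 7.9.2.3. This belongs in the same edit, because a seed and a fixed number alone do not settle a near-threshold verdict.

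The cost is a few lines of SAP text before database lock and negligible computing time. No change to conduct, data collection or sample size is needed.
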